### Secondary Analyses

- 1) If sample size allows, stratify analyses by mechanical ventilator use prior to or at the index date
- 2) If sample size allows, subgroup analyses comparing patients who received convalescent plasma and remdesivir, with those who only received remdesivir.
- 3) If sample size allows, stratify analyses by time interval from hospital admission to the index date (<72 hours vs. ≥72 hours).
- 4) If sample size allows, stratify analyses by disease severity measured by oxygenation.

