### Cohort Sampling

This is a retrospective cohort study with risk-set sampling for exposure status of convalescent plasma using EHRs in the Baylor Scott & White Health (BSWH) healthcare delivery system. In brief, patients who received convalescent plasma will be matched to a similar population who did not receive convalescent plasma around the same time ( $\pm 2$  days) of transfusion across sites. The administration date of convalescent plasma for the treated population and the matched date for the untreated population are thereafter referred as the index date. The matching scheme for risk-set sampling is defined in step-by-

step points in the following paragraph. The follow-up for the matched cohort will start from the index date and continue until the end of the observation period. The observation period for this study is defined as at least 28 days from the index date. In other words, the index date must be at least 28 days prior to the date of data pull to allow for adequate follow-up and minimize selection bias from informative censoring due to death or discharge for palliative care. An unexposed patient at the index date could receive convalescent plasma during the follow-up and the follow-up will be censored at the administration date of convalescent plasma (Figure 1).

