**Figure 1. Schematic diagram for retrospective cohort study with risk-set sampling for convalescent plasma exposure**

CP= convalescent plasma

\* Hospital admission includes the earliest encounters at emergency or inpatient departments around COVID-19 confirmation within  $\pm 14$  days.

† The earliest possible date is July 1st, 2020.

Step-by-step risk-set sampling with replacement for the retrospective cohort design to account for confounding and to strategize EHR abstraction at BSWH:

1. Identify patients hospitalized with laboratory-confirmed COVID-19 (Source population)

The study population will be patients with laboratory-confirmed COVID-19 (i.e., RT-PCR test results recorded by the BSWH laboratory informatics systems and/or the EHR system) and received or matched to a patient who received convalescent plasma from July 1st to September 28th. Patients must have at least 28 days of observation opportunity from the date of data pull to the index date (reverse order). Patients cannot have been previously admitted into hospitals due to RT-PCR laboratory confirmed COVID-19.

2. Identify patients who received convalescent plasma (Exposed group)

Blood bank records will be scanned to identify patients who had at least one order to transfuse COVID-19 convalescent plasma using the International Society of Blood Transfusion (ISBT) 128 codes (Appendix 1). The order will be linked to the administration record of the plasma to determine the date and time the product was given.

3. Risk-set sampling and matching variables (Unexposed group)

For each patient who received a first dose of convalescent plasma, we will sample from the source population who did not receive convalescent plasma (Unexposed group) at the same calendar time ( $\pm 2$  days) and match on the following variables. One patient could be sampled at maximum twice; first sampled into the unexposed group and later sampled into the exposed group due to initiation of convalescent plasma transfusion during follow-up.

- Calendar date around the index date within  $\pm 2$  days: Risk-set sampling to match exposed and unexposed patients will account for this factor
- Age ( $\pm 5$  years)
- Sex (female, male)
- Days from hospital admission to the index date

4. Propensity score matching and baseline covariates

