### **Covariates**

Covariates including those for risk-set sampling and propensity score matching (See Cohort Sampling) will be assessed during baseline and are listed in Appendix 2. Baseline is defined as the period prior to and including the index date. For variables (e.g., vital signs and comedications) assessed at multiple time points, the value closest to the index date will be used. However, for oxygenation, the worst measures 4-12 hours prior to the index date will be used. For variables (e.g., cardiovascular conditions) that are usually collected at hospital admission or possibly in previous healthcare encounters for other health concerns, the value will be searched in the past year from and including the hospital admission date, unless specified otherwise. The lookback period for each covariate is listed in Appendix 2.

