A Cox proportional hazards regression will estimate HRs and 95% CIs using the propensity score-matched cohort for the secondary outcomes of ICU transfer and mechanical ventilation. Patients will be followed from the index date until the earliest of the following: 1) the outcome of interest, 2) death, 3) discharge alive, 4) day 28 since the index date, or 5) the date of unexposed patients who were administered COVID-19 convalescent plasma.

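### The index is a calendar date that counts as both baseline and follow-up, so ventilation on the day of transfusion can fall on the wrong side of treatment

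*Protocol*

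**What the plan says.** The Protocol's Cohort Sampling section defines the index as a date: "The administration date of convalescent plasma for the treated population and the matched date for the untreated population". Step 2 of the sampling scheme links the plasma order to the administration record to "determine the date and time the product was given", but the index is not defined by that time. Comparators have a matched date only.

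Three kinds of rule are tied to that date:

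- **Baseline.** The Covariates section states "Baseline is defined as the period prior to and including the index date", and the propensity score step defines baseline in the same way. Item 1 of Secondary Analyses would, sample size permitting, "stratify analyses by mechanical ventilator use prior to or at the index date".
- **Follow-up.** Cohort Sampling states "The follow-up for the matched cohort will start from the index date and continue until the end of the observation period". For ICU transfer and mechanical ventilation, Comparative Analyses states "Patients will be followed from the index date until the earliest of the following: 1) the outcome of interest, 2) death", and then lists discharge, day 28 and later plasma in a comparator.
- **Severity.** The Covariates section makes an exception to the general baseline rule: "for oxygenation, the worst measures 4-12 hours prior to the index date will be used". Appendix 2 repeats this window. Appendix 3 includes invasive ventilation as a level of the oxygenation scale, so ventilation status enters the propensity score through this window.

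**The concern.** The index date belongs to baseline and to follow-up at once. Plasma is given at some hour on that date, so an intubation on the same date may come before or after it, and nothing in the protocol says which side it belongs to.

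Two analyses are directly exposed. In the item 1 stratification, an intubation that follows transfusion can define a baseline stratum, so the comparison is conditioned on something treatment may have influenced. This reaches mortality as well as the secondary outcomes, because item 1 is not limited to one endpoint. In the overall ventilation analysis, an intubation that preceded transfusion, and may have prompted it, can be counted as an event after plasma. ICU transfer has the same follow-up rule. Neither outcome is restricted to patients still at risk of it.

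The severity window adds a third problem. It closes at least four hours before the index, so the propensity score can miss deterioration just before plasma. Confounding by indication is most worrying in that period, and the Limitations section acknowledges such confounding.

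**Working it through.** The protocol gives no figure to reproduce here. The check sets its windows side by side and then illustrates the size of the effect on assumed rates.

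**Step 1. Place the same ventilation under each rule, reading the index as a calendar date**

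| Ventilation begins | Item 1 stratum | Ventilation outcome | 4-12 hour severity covariate |
|---|---|---|---|
| Index date, before transfusion | ventilated | can count as an event | missed |
| Index date, after transfusion | ventilated | can count as an event | missed |
| Before the index date, still ventilated | ventilated | not excluded; status undefined | captured if present in the window |

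In the first row the event role is wrong. In the second the stratum role is wrong. That index-date ventilation counts as an event is an inference: follow-up starts on that date and no exclusion is given. The protocol does not say it outright.

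**Step 2. The severity gap under both readings of the index**

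- Index as a clock time: ventilation begun in the last 4 hours before transfusion is in the stratum but not in the covariate.
- Index as a date starting at midnight: the window runs from 24 − 12 = 12:00 to 24 − 4 = 20:00 on the previous day. For a transfusion at, say, 18:00, the unmeasured gap is 4 + 18 = 22 hours.

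**Step 3. Illustration for the overall ventilation outcome**

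Assumptions, none from the protocol: plasma has no effect; 28-day ventilation risk among patients not ventilated at time zero is p = 0.15; a fraction e of recipients is intubated on the index date before transfusion and counted as an event, with none in comparators.

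Recipients' apparent risk = e + (1 − e) × p. The e already intubated cannot also carry the later risk, so p applies only to the remainder. The apparent hazard ratio is approximated by the ratio of cumulative hazards, ln(1 − apparent risk) / ln(1 − p).

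- e = 0.01: risk = 0.01 + 0.99 × 0.15 = 0.1585; HR = ln(0.8415)/ln(0.85) = 1.06
- e = 0.02: risk = 0.02 + 0.98 × 0.15 = 0.167; HR = ln(0.833)/ln(0.85) = 1.12
- e = 0.03: risk = 0.03 + 0.97 × 0.15 = 0.1755; HR = ln(0.8245)/ln(0.85) = 1.19

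**Step 4. Wider assumptions**

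Let a fraction u of comparators also have such events, so HR = ln[(1 − e)(1 − p)] / ln[(1 − u)(1 − p)]. Four pairs (e, u) were tried, from (0.01, 0.005) to (0.05, 0.01):

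- p = 0.05: 1.09 to 1.67
- p = 0.10: 1.05 to 1.36
- p = 0.20: 1.02 to 1.18

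The distortion grows as true ventilation becomes rarer and as the same-day imbalance widens.

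**The case against.** The best defence is that the index is meant as a clock time. The severity window is in hours, item 3 of Secondary Analyses splits at 72 hours from admission, and the transfusion time is extracted. On that reading, use up to the index is prevalent ventilation, follow-up is what comes after, and the two do not overlap for recipients. This has weight as a guess at intent, but the protocol never states it. It also leaves comparators without a time, since they are matched on calendar date and on days from admission. The last four hours before transfusion would still be missing from the severity covariate.

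It can also be said that day-zero ordering belongs in a separate plan, or in the Appendix 4 data table, which is still to be filled in. But Section IV is itself the statistical analysis plan, and the difficulty lies in rules it states.

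Item 4 stratifies by oxygenation. If it uses the pre-index scale, intubation after transfusion cannot contaminate it. It does not repair item 1 or the ventilation outcome.

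Other objections limit the point and are right. Item 1 is conditional on sample size. It can be read as an ever-ventilated stratum, so including a patient already extubated is a choice of definition and not a contradiction. Matching is on the propensity score within a caliper, not exactly on oxygen support, so matched sets can split across strata whichever ventilation variable is used. That splitting is no evidence of this fault.

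**Conclusion.** The point holds as an ambiguity with consequences. The index date lies in both baseline and follow-up, same-day events are not ordered, and the ventilation and ICU-transfer outcomes have no at-risk rule. Same-day intubations can therefore fall on the wrong side of treatment, and the propensity score can miss ventilation begun shortly before plasma. This should be corrected before analysis.

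A reader might infer three stronger things that the protocol does not support:

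- **That every same-day intubation is misplaced in practice.** This depends on how the index is implemented, and a time-stamped implementation would remove the overlap for recipients.
- **That early harm from plasma is hidden.** The item 1 stratum moves such patients to the other stratum, but the overall ventilation analysis still counts them. TRALI and TACO are also identified and reported separately by diagnosis code.
- **That the primary result is undermined.** The unstratified 28-day mortality analysis is affected only through severity adjustment.

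The apparent hazard ratio of about 1.12 (1.06 to 1.19) under no true effect rests wholly on the assumed 15% risk and 1-3% excess. Other plausible inputs gave 1.02 to 1.67. These figures show that the distortion could be material for the ventilation outcome; they do not estimate it for this cohort.

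**What to change.** Define one index date and time for every patient and use it in every rule:

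1. For recipients, use the start of transfusion, based on the administration time already extracted in step 2 of the sampling scheme. For each comparator, use the same elapsed time since admission as the matched recipient.
2. Define baseline and the item 1 stratum by status at or before that time.
3. Count ventilation, ICU transfer and death only after it.
4. Restrict the ventilation outcome to patients not already ventilated at that time, and the ICU-transfer outcome to patients not already in ICU.
5. Run the oxygenation covariate up to that time, or keep its window and add ventilation status at time zero to the propensity score.

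The wording changes fall in Cohort Sampling, Covariates, Comparative Analyses, Secondary Analyses item 1 and Appendix 2. The cost is some programming with EHR time stamps and smaller at-risk sets, hence less precision, for the ventilation and ICU outcomes. No new data collection is evident.

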### Sensitivity Analyses

- 1) To assess the COVID-19 cohort definition of hospital admission within ±14 days of laboratory confirmed COVID-19 diagnosis, we will further restrict the source population to those who were admitted into affiliated BSWH hospitals within ±7 days of laboratory confirmed COVID-19 diagnosis. This is because COVID-19 could progress quickly and patients could also transfer to hospitals outside of the network of BSWH with a large time window around COVID-19

confirmation resulting in potential residual confounding by severity and survivor bias by prior treatment

- 2) Instead of ending the observation period at 28 days since the index date, we will continue follow-up until the end of the study period, unless an outcome event occurs earlier. Patients will be followed from the index date until the earliest of the following: 1) death, 2) discharge alive, 3) the end of the study period, or 4) the date of unexposed patients who were administrated COVID-19 convalescent plasma.
- 3) Given that mortality data after hospital discharge is limited and that patients could be discharged for palliative care due to disease worsening, the outcome “discharge alive” will be considered a competing risk for 28-day in-hospital mortality. To account for competing risk of in-hospital death and discharge alive, sub-distribution hazard ratios will be estimated from the Fine-Gray model. Cumulative incidence function will be estimated by modeling the cause-specific hazard function of all causes.

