### Study Outcomes

- Safety

Safety events related to plasma transfusion were selected from the Centers for Disease Control and Prevention (CDC) National Healthcare Safety Network (NHSN) Biovigilance Component Hemovigilance Module Surveillance Protocol.a The following safety outcomes will be identified by ICD-10-CM billing codes (Appendix 5).

- Transfusion associated circulatory overload (TACO)
- Transfusion-related acute lung injury (TRALI)
- Anaphylactic reaction

---

a The following events were excluded because they are irrelevant for plasma transfusion or because there are no transfusion-specific billing codes. Transfusion-associated graft vs. host disease (TAGVHD) is associated with a cellular product. Delayed hemolytic transfusion reaction (DHTR) and delayed serologic transfusion reaction (DSTR) are associated with red cells containing products. Post transfusion purpura (PTP) is associated with platelets containing products. No transfusion specific billing codes exist for transfusion-associated dyspnea (TAD) allergic reaction and hypotensive transfusion reaction.

- Febrile non-hemolytic transfusion reaction
- Transfusion-transmitted infection
- Acute hemolytic transfusion reaction
- A composite outcome of thrombotic or thromboembolic complication including stroke, myocardial infarction, venous thromboembolism, deep vein thrombosis, and pulmonary embolism
- A composite outcome of cardiac arrhythmias including ventricular tachycardia, ventricular fibrillation, atrial arrhythmia, and cardiac arrest
- Effectiveness
  - Primary:
    - 28-day in-hospital mortality
  - Secondary:
    - Discharge alive
    - ICU transfer
    - Mechanical ventilation

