#### Comparative Analyses

A Kaplan-Meier curve will be plotted using the propensity score matched cohorts. To control for measured confounding, patients will be sampled in risk sets with replacement and propensity score matched. Distribution of covariates between exposure groups before and after propensity score matching will be assessed to evaluate the balance of baseline covariates and potential residual confounding. Absolute standardized differences, the differences in means or proportions divided by the pooled standard deviation, will be computed for each covariate to check its distribution balance within exposure groups. Covariates with an absolute standard difference greater than 0.1 will be further controlled in the analyses by including specific variables in the Cox model.

The adjusted incidence rates of death in the first 7, 14, 21, and 28 days after the index date will be estimated for the exposed and unexposed groups using the propensity score-matched cohort.

For the primary outcome (28-day in-hospital mortality), a Cox proportional hazards regression will estimate hazards ratios (HRs) and 95% confidence intervals (CIs) using the propensity score-matched cohort. Patients will be followed from the index date until the earliest of the following: 1) death, 2) discharge alive, 3) day 28 since the index date, or 4) the date of unexposed patients who were administered COVID-19 convalescent plasma. Patients discharged alive will be censored at the discharge date. The proportional hazards assumption will be evaluated using Schoenfeld residuals test and visual inspection of log-log plots.

For the secondary outcome of discharge alive, we will not censor the follow-up at the date of in-hospital death but will censor at day 28 to account for this worst possible outcome and to account for the competing risk of in-hospital death. In other words, patients will be followed from the index date until the earliest of the following: 1) discharge alive, 2) day 28 since the index date, or 3) the date of unexposed patients who were administered COVID-19 convalescent plasma.

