**VI. LIMITATIONS**

Unmeasured confounding

Given that patients were not randomly assigned to receive convalescent plasma, confounding by indication may not be fully accounted for using the available data elements in EHRs. Missing data and misclassification for covariates may result in residual confounding and biased risk estimates. For example, the convalescent plasma exposed group may appear to have a more favorable clinical outcome compared to the unexposed group, because the unexposed group had more severe disease to start with, and the two groups were not comparable at the index date. Alternatively, the exposed group may appear to have no favorable clinical outcomes or even worse outcomes, because patients in this group started with more severe disease at the index date.

Although risk-set sampling and propensity score matching are used to control measured confounding, EHRs are not able to fully capture all important prognostic factors related to outcomes of interest. To evaluate the possible impact of unmeasured confounding, we will consider exploring some of the methods listed below if feasible.

- Quantitative bias analyses
- Negative outcome controls
- E-values 
- Instrumental variables

Informative censoring

Treatment switches or hospital transfers during follow-up may be related to worsening of COVID-19. To evaluate this potential selection bias, we will use an intent-to-treat (ITT) analysis, whereby treatment switches will not censor the follow-up and instead fixed duration of follow-up will be used. Reasons for and where patients were transferred will be assessed according to exposure groups.

Effect modification by antibody titer

This observational study does not impose the inclusion criterion of seronegative for SARS-CoV-2 because testing antibody titers before administering convalescent plasma is not the present routine clinical practice at BSWH. Hence, individual antibody titers/humoral immunity in patients is not accounted for. The neutralizing capacity of convalescent plasma received by patients is not tested nor captured in the EHRs. In addition, the effective level of neutralizing titers inpatients who have received passive antibody therapies is also unknown. If a limited or no association between convalescent plasma and the clinical outcomes are observed, the results may not be interpreted as a true “no effect” of convalescent plasma due to the uncertainty of the titer values.

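### Palliative discharge is pooled with recovery: it counts as a favourable discharge alive, and the 28-day window does not correct for it

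*Protocol*

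**What the plan says.** The primary effectiveness outcome is "28-day in-hospital mortality" (Protocol, Study Outcomes). In the Cox model for it, follow-up stops at the earliest of death, live discharge, day 28 or, for unexposed patients, a later plasma transfusion. The rule for discharge has no exception: "Patients discharged alive will be censored at the discharge date" (Comparative Analyses). Follow-up for ICU transfer and mechanical ventilation also ends at live discharge.

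"Discharge alive" is listed as a secondary effectiveness outcome (Study Outcomes) and is not split by reason or destination. For it, "we will not censor the follow-up at the date of in-hospital death but will censor at day 28" (Comparative Analyses), so that in-hospital death is held as the worst result.

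The protocol also describes the patients at issue. Sensitivity Analyses, item 3, says that "patients could be discharged for palliative care due to disease worsening" and that "mortality data after hospital discharge is limited". It responds by making live discharge, as one category, a competing event in a Fine-Gray model. Cohort Sampling says that the 28 days required between index date and data pull serve to "minimize selection bias from informative censoring due to death or discharge for palliative care".

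**The concern.** The protocol attributes palliative discharge to worsening, then handles it exactly as it handles recovery. For the secondary outcome, a patient sent out to die scores the same as one who goes home well. For the primary outcome, that patient leaves the risk set just as the hazard of death is likely to be highest, and the later death is unlikely to be recorded.

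Exposure was not randomised. If decisions about palliative care differ between patients given plasma and those not given it, the loss of imminent deaths is unequal and can create or mask an apparent effect on mortality. A reader of Cohort Sampling would also believe that the 28-day requirement protects against this.

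**Working it through.** **Step 1. Follow one palliative discharge through each rule.**

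| Analysis | Treatment of a palliative discharge | Separated from recovery? |
|---|---|---|
| Primary Cox and Kaplan-Meier (Comparative Analyses) | Censored at discharge | No |
| Discharge alive (Study Outcomes, Comparative Analyses) | Favourable event | No |
| ICU transfer, ventilation (Comparative Analyses) | Follow-up ends at discharge | No |
| Sensitivity analysis 2, longer follow-up | Follow-up still ends at discharge | No |
| Sensitivity analysis 3, Fine-Gray | Competing event, pooled | No |
| Intent-to-treat analysis (VI. Limitations) | Lifts censoring for treatment switches; palliative discharge not named | No |

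**Step 2. The 28-day window.** It guarantees that 28 days have elapsed before the data pull. The Cox rule stops observation at discharge, so for a patient discharged on day 10 the remaining 18 days are never used. The window deals with administrative truncation, not with palliative discharge.

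**Step 3. Size, by illustration.** The protocol states no figure for palliative discharge, so there is none to reproduce. The Section V sample sizes are not in question here.

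Inputs:
- 28-day deaths without plasma: 1 − 0.75 = 0.25 (Section V).
- Assumed: no true effect, so 0.25 in both groups.
- Assumed: 90% of the other patients are discharged recovered by day 28, 0.90 × 0.75 = 0.675.
- Assumed: a share q of those who die leave first for palliative care.
- Assumed: constant cause-specific hazards.

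Formulas: in-hospital deaths = 0.25 × (1 − q); discharged alive = 0.675 + 0.25 × q. The fraction still in hospital at day 28 is 1 − 0.925 = 0.075 in both groups, so the total hazards are equal and the Cox hazard ratio for death is the ratio of in-hospital deaths. The Fine-Gray ratio is approximated by ln(1 − deaths, exposed) / ln(1 − deaths, unexposed).

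- q = 10%: deaths 0.225, discharged alive 0.700.
- q = 20%: deaths 0.200, discharged alive 0.725.
- q = 30%: deaths 0.175, discharged alive 0.750.

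| q unexposed / exposed | Cox HR, death | Fine-Gray, approx. | Ratio of proportions discharged alive |
|---|---|---|---|
| 10% / 10% or 20% / 20% | 1.00 | 1.00 | 1.00 |
| 10% / 20% | 0.200/0.225 = 0.89 | ln 0.800 / ln 0.775 = 0.88 | 0.725/0.700 = 1.04 |
| 20% / 10% | 0.225/0.200 = 1.125 | 1.14 | 0.97 |
| 10% / 30% | 0.175/0.225 = 0.78 | ln 0.825 / ln 0.775 = 0.75 | 0.750/0.700 = 1.07 |
| 30% / 10% | 1.29 | 1.32 | 0.93 |

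With a true relative risk of 0.7 and equal q, the Cox hazard ratio is 0.68, the same as with no palliative discharge at all.

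**Step 4. Misclassification that needs no imbalance.** At q = 10% in both groups, 0.025/0.700 = 3.6% of the events counted as discharge alive are palliative; at q = 20%, 0.050/0.725 = 6.9%.

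**Step 5. Does the composite remove the distortion?** For 10% / 20%, in-hospital death or palliative discharge is 0.225 + 0.025 = 0.250 against 0.200 + 0.050 = 0.250, a ratio of 1.00. This holds by construction, because the illustration lets every palliative discharge end in death within 28 days.

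**The case against.** The strongest defence is that the endpoint is in-hospital death. A death after discharge is not an event by definition, and a Cox model that censors at discharge still estimates a defined cause-specific hazard. That stands. A reader might infer that the primary analysis scores dying patients as good outcomes. It does not: it censors them, and only the secondary outcome scores them favourably.

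The protocol also does not ignore the issue. It names informative censoring and offers the Fine-Gray model in response. A reader might object that this model supposes a palliative discharge never dies. It supposes only that the patient can no longer die in hospital, which is right for this endpoint. What remains is narrower: palliative and recovery discharges form one competing event, so the analysis carries about the same distortion as the Cox model in Step 3.

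It is also tempting to say that transfers out for worsening count as discharged alive. The text does not classify them so. VI. Limitations treats transfers separately: "Reasons for and where patients were transferred will be assessed according to exposure groups".

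Finally, definitions of data elements are deferred to Appendix 4, so a missing code for disposition is no error in itself. But Section IV already fixes the pooling, and a coding table would not undo it.

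**Conclusion.** The concern holds in limited form. Palliative discharge, which the protocol itself links to worsening, is pooled with recovery in every analysis of effectiveness, and the 28-day window does not do what Cohort Sampling claims for palliative discharge. The secondary outcome is misclassified regardless of exposure group; under the assumed shares of 10% to 20%, about 4% to 7% of its events are affected.

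Bias in the relative effect on death is conditional. It needs palliative discharge to differ by exposure, and neither its size nor its direction can be derived from the protocol. A reader might infer that the plan hides a benefit of plasma, or manufactures one. The document supports neither: in the illustration the hazard ratio stays at 1.00 with equal shares and moves to about 0.89 or 1.12 as the imbalance runs one way or the other. For scale, the relative risks in Table 1 run from 0.61 to 0.81, so a shift of about 0.1 would matter to interpretation. All of these figures rest on the assumed shares, the assumed 90% recovery discharge and constant hazards. The point should be corrected, but it does not invalidate the primary analysis.

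**What to change.** 1. Abstract discharge disposition from the EHR and define it in Appendix 4.
2. Define the favourable secondary outcome as live discharge other than to palliative or hospice care. Carry palliative discharges to day 28 without the event, as Comparative Analyses already does for in-hospital death.
3. Add to Sensitivity Analyses a named analysis of in-hospital death or palliative discharge by day 28, using the same matched Cox model. The primary analysis can stay as it is.
4. Reword Cohort Sampling so that it no longer credits the 28-day window with minimising bias from palliative discharge.

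The cost is one more EHR field, which the review of transfers in VI. Limitations already partly needs, and slightly fewer favourable discharges in each group.

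### Palliative discharges are never separated from recoveries, so unequal palliative discharge between groups would distort both in-hospital mortality and discharge alive

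*Protocol*

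**What the plan says.** The primary effectiveness outcome is "28-day in-hospital mortality" (Study Outcomes). In the primary Cox model, "Patients discharged alive will be censored at the discharge date" (Comparative Analyses), with no exception for the reason for discharge.

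Discharge alive is also a secondary outcome, where it is the event. There, patients who die in hospital are kept at risk: the plan "will censor at day 28 to account for this worst possible outcome" (Comparative Analyses).

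The protocol knows that not every live discharge is a recovery. Sensitivity Analyses item 3 says that "mortality data after hospital discharge is limited" and that "patients could be discharged for palliative care due to disease worsening". It offers two safeguards:

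- **The 28-day interval.** Cohort Sampling requires an index date at least 28 days before the data pull, in order to "minimize selection bias from informative censoring due to death or discharge for palliative care".
- **Fine-Gray.** Under Sensitivity Analyses item 3, discharge alive "will be considered a competing risk for 28-day in-hospital mortality", as a single undivided category.

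Section VI (Limitations), under informative censoring, adds an intent-to-treat analysis in which "treatment switches will not censor the follow-up and instead fixed duration of follow-up will be used", and a review of transfer reasons and destinations by exposure group.

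**The concern.** A patient sent home or to hospice to die and a patient who has recovered are handled identically in every planned effectiveness analysis. In the mortality analyses, the death that follows a palliative discharge is never seen. In discharge alive, the same patient is a success, although someone equally ill who dies on the ward is held to day 28 as the worst result. The premise in Sensitivity Analyses item 3 and the event definition in Comparative Analyses do not fit together.

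Neither safeguard closes the gap. Follow-up ends at discharge, so time between the index date and the data pull adds no information about a patient who has left. Fine-Gray changes how discharge enters the risk set but does not distinguish one kind of discharge from another.

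Treatment was not randomised, and Appendix 2 lists no covariate for goals of care or limits on treatment. Palliative discharge could therefore differ between the matched groups for reasons unrelated to plasma, and part of that difference would be read as an effect of plasma.

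**Working it through.** **1. The plan's own figure.** Table 1 supplies the yardstick. Section V rules out rows needing more than 729 plasma patients, so the weakest attainable effect is 0.78 (2,500 in total, 1:3). Freedman's log-rank formula reproduces it, reading the ratio as one of 28-day risks:

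- Plasma risk p1 = 0.78 × 0.25 = 0.195; HR = ln(0.805)/ln(0.75) = 0.754.
- Deaths d = 2,500 × (0.25 × 0.195 + 0.75 × 0.25) = 590.6.
- With φ = 1/3: √(dφ) × (1 − HR)/(1 + φHR) − 1.96 = 14.03 × 0.246/1.251 − 1.96 = 0.80, so power is 0.79.

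All 16 rows reproduce this way, with power 0.788 to 0.812. Table 1 is not in dispute. Inverted, 0.78 is 1.28 and the stated target of 0.7 is 1.43.

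**2. Apparent mortality ratio under no effect.** Let a poor outcome be in-hospital death or palliative discharge by day 28, equally likely in both groups. Let h1 (plasma) and h0 (unexposed) be the shares of poor outcomes that leave for hospice. The in-hospital death ratio is (1 − h1)/(1 − h0), and the overall risk cancels. The shares are assumptions: h0 = 20-30%, h1 = 10-15%.

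- Smallest distortion: 0.85/0.80 = 1.06.
- Largest distortion: 0.90/0.70 = 1.29.

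With the two groups exchanged, the ratios invert to 0.94 and 0.78. With h1 = h0 the ratio is 1.00.

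**3. All three analyses together.** Take the 25% mortality implied by Section V. Assume no plasma effect, that every palliative discharge dies by day 28, recovered discharge in 65% of each group, and constant cause-specific hazards. In each group 90% have then died or left by day 28, so the total hazard is equal and the Cox ratio is the ratio of in-hospital deaths. The Fine-Gray and discharge-alive ratios are close to ln(1 − F1)/ln(1 − F0), where F is the cumulative incidence at day 28.

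For palliative discharge of 5% (plasma) and 2% (unexposed), in-hospital death is 20% and 23%, and discharge alive is 70% and 67%:

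- Cox: 20/23 = 0.87.
- Fine-Gray: ln(0.80)/ln(0.77) = 0.85.
- Discharge alive: ln(0.30)/ln(0.33) = 1.09.

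| Palliative discharge, plasma vs unexposed | Cox | Fine-Gray | Discharge alive |
|---|---|---|---|
| 2% vs 2% | 1.00 | 1.00 | 1.00 |
| 5% vs 2% | 0.87 | 0.85 | 1.09 |
| 8% vs 3% | 0.77 | 0.75 | 1.15 |
| 2% vs 5% | 1.15 | 1.17 | 0.92 |
| 3% vs 8% | 1.29 | 1.33 | 0.87 |

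In each unequal row the three results agree on the same wrong conclusion, and Fine-Gray lies slightly further from 1 than Cox.

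**4. Chance of a false positive.** With 400 plasma and 1,600 unexposed patients and in-hospital death of 20% vs 23%, a two-proportion test has pooled SE 0.0233 and unpooled SE 0.0226. Then (0.03 − 1.96 × 0.0233)/0.0226 = −0.69, a 24% chance of false benefit. The reverse, 23% vs 20%, gives a 27% chance of false harm. The nominal two-sided level is 5%.

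**5. After separating palliative discharge.** In every row the composite of in-hospital death or palliative discharge is 25% in both groups, and recovered discharge is 65% in both. All ratios return to 1.00.

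**The case against.** The declared endpoint is in-hospital mortality, and Fine-Gray is a valid model for its incidence when discharge precludes it. This stands. A reader might infer that the Fine-Gray analysis is an error; it is not, but it does not deal with the palliative discharges given as a reason for it.

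The 28-day interval has a proper purpose: it stops recent index dates being cut short by the data pull. This also stands. Only the claim about palliative discharge fails.

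The sizes rest on assumed hospice rates. The documents give neither a rate nor a difference between groups, and if some of these patients survive to day 28 the mortality distortion shrinks in proportion. This stands. What is shown is a mechanism and a plausible range, not a demonstrated bias.

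A reader might also infer that the distortion is as large as the effect sought. The figures do not support that: under the assumed shares only the extreme corner (1.29) passes the weakest attainable row of Table 1 (1.28 inverted), and nothing reaches 1.43.

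Nor can one say that nothing planned would reveal the problem. The transfer review in Section VI might show an imbalance, although it does not name hospice. It corrects no estimate. The intent-to-treat analysis concerns treatment switches, and the extended follow-up in Sensitivity Analyses item 2 also stops at discharge.

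**Conclusion.** The point holds as a should-fix. The plan recognises palliative discharge due to worsening but never separates it from recovery, and neither safeguard offered for it works for that purpose.

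It would be too strong to say that palliative patients count as favourable throughout. That is literally so only for the secondary outcome; in the primary Cox model they are censored, which hides the death rather than scoring a success. It would also be wrong to infer a known direction: the error can favour plasma or count against it, and under no effect it vanishes when rates are equal.

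Under the assumed shares (20-30% of poor outcomes among unexposed, 10-15% among plasma patients), a true null would read as a risk ratio of 1.06 to 1.29. Because Cox, Fine-Gray and discharge alive shift together, their agreement would offer no reassurance.

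**What to change.** Using discharge disposition, if the health record holds it (Appendix 4 is an unfilled template, so this needs confirming):

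- **Discharge alive:** exclude discharges to hospice or palliative care from the event, and treat them as in-hospital deaths are treated in that analysis.
- **Mortality:** leave the primary outcome unchanged and add one sensitivity analysis whose event is in-hospital death or discharge to hospice or palliative care by day 28.
- **Reporting:** tabulate hospice and palliative discharges by exposure group.
- **Cohort Sampling:** remove the statement that the 28-day interval minimises bias from palliative discharge, and keep the interval itself for adequate follow-up.

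The cost is one data field, one extra model, one table and a few lines of text. The drawback is that the composite counts some patients who would have survived past day 28, which is why it belongs beside the primary analysis and not in its place.
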